3.2 Secondary Objectives

- a. To determine the prevalence and incidence of MRSA colonization of the nares, throat, perirectal, axilla, and groin areas among HIV infected patients and to study changes in the colonization rates over time.
- b. To determine the predictors of MRSA colonization and infection among HIV-infected persons including examination of demographics, sexual activity, hygienic practices, drug use, antibiotic and antiretroviral medications, sexually transmitted diseases, and HIV control.
- c. To evaluate the change in CD4 counts and HIV viral loads during the time of a MRSA or soft tissue infection.
- d. To characterize the molecular characteristics and the antimicrobial sensitivities of MRSA isolates in this population.
- e. To continue the previous retrospective study of MRSA infections among HIV-infected persons to examine the incidence of and describe the clinical features of MRSA infections and their response to treatment among HIV-infected patients seen within the HIV clinic at NMCSD. This study also will continue to compare those with and without MRSA infections in terms of demographic data, HIV viral loads, CD4 counts, and use of medications including antiretroviral and antimicrobial agents.

IV. BACKGROUND AND SIGNIFICANCE

MRSA was first recognized in 1961 and subsequently became a frequent cause of infections within the hospital setting. The first community-acquired MRSA infections occurred in the early 1980s. Within the past several years, the number of community-acquired MRSA cases has dramatically increased with incidence rates of 18 to 26 cases per

100,000 persons [1, 2]. In addition to individual cases, numerous outbreaks have occurred among prison inmates, athletes, military trainees, and men who have sex with men (MSM) [14-18].

Patients presenting with community-acquired MRSA infections typically present with skin or soft tissue infections such as folliculitis, furuncles, carbuncles, abscesses, or cellulitis [1, 7]. Despite that most of these infections occur in young, otherwise healthy individuals, community-acquired MRSA infections have led to a high hospitalization rate with up to 25% requiring admission for the management of the MRSA infection [1].

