- (2) Is the treatment effect different for repeat administrations of hexachlorophene/mupirocin? The rate of MRSA positive versus negative for recolonization reoccurrence through the sequence 1 versus 2 versus 3 versus 4 treatments will be assessed by a test of trend.
- (3) Is there a persistent or repeated-treatment effect? The overall rates of MRSA recolonization at 6, 12, 18, and 24 months will be assessed by a test of trend.
- (4) Is there an individual propensity for susceptibility and what are the treatment differences between placebo and hexachlorophene/mupirocin in terms of length of time for being negative for MRSA colonization on repeated testing? A Kaplan-Meier long-rank test will be conducted on three groups: initially negative, initially positive treated with hexachlorophene/mupirocin, and initially positive treated with placebo, where survival is defined as not having acquired MRSA.

For the secondary objectives, part (a) will be assessments of the rates in which prevalence is defined as the number of patients colonized with MRSA at the beginning of

the study divided by the total population studied, and the incidence as the number of new infections per calendar time divided by the total population studied. For objective (b) examining for predictors of MRSA, we will create a multivariate logistic regression model and use a backward stepwise approach. For part (c), to evaluate if there is a significant change in the CD4 count and/or viral load pre- versus during a MRSA infection we will utilize a 1-way ANOVA. We will also compare pre-MRSA infection with after MRSA resolution as well as the counts during the infection with those after resolution. Finally, objective (d) will be a descriptive analysis of the molecular and microbiologic characteristics of the isolates. The main statistical data from the retrospective chart review study of HIV patients at NMCSD will be presented by descriptive analyses. We will compare demographics and HIV clinical data between those with and without MRSA using rank sum tests and Fisher's exact tests depending on the variable characteristics (categorical or continuous). A multivariate logistic regression model for predictors of MRSA will then be developed using a backward stepwise approach using Stata software.

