Using these data, we proposed a sample size of 500 participants to find statistically significant results; given the long duration of follow-up and the possibility for attrition, we will enroll 550 participants accounting for 50 drop-outs.

Overall, we plan to enroll 550 participants into the study with the goal of a minimum of 50 randomizations for scientific significance. In addition, we will also examine unique randomizations, defined as a subject's initial randomization (not counting re-randomizations), as a sub-analysis of the primary endpoint. Of note since the primary endpoint includes completion of the 6 month follow-up visit after initial randomization, at least 50 subjects with these data are needed.

We plan to conduct an interim examination yearly (after at least one-half of subjects are enrolled) to determine the adequacy of the design assumptions and sample size, given that there is little literature regarding the expected colonization and infection rate in this specific (HIV) population. Also, approximately every year we will conduct an examination of the epidemiologic data regarding the prevalence and incidence of MRSA in this cohort, as well as a safety assessment.

We also calculated a sample size for the secondary objective which was to determine the predictors of MRSA colonization and infection among HIV-infected persons including examination of demographics, sexual activity, hygienic procedures, drug use, antibiotic and HAART medications, sexually transmitted diseases and HIV control. Of note, the other secondary objectives do not lend themselves to sample size calculation due to the paucity of baseline data in the literature. Predictors for MRSA were examined in three studies including Mathews et al, Lee et al, and our retrospective work [7, 12, 13]. For a power at 80%, alpha of 0.05, and examining 20 potential predictors with an R^2 of 0.10, we would need to enroll 205 patients in the study (sample power analysis, SPSS). As we examined more predictors, a larger sample size (500 to 550) is preferred.

VIII. DATA ENTRY AND ANALYSES

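### Secondary objective (b) names predictors of MRSA by backward stepwise selection among 20 or more candidates, with no stated retention level, validation or exploratory label; at a 0.05 level, noise alone would usually yield a predictor

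*Combined protocol and SAP*

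**What the plan says.** Section 3.2(b) sets the aim: "To determine the predictors of MRSA colonization and infection among HIV-infected persons". It lists broad groups of candidates: demographics, sexual activity, hygiene, drug use, medications, sexually transmitted diseases and HIV control.

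Section VII gives the method in one clause: "we will create a multivariate logistic regression model and use a backward stepwise approach". The same method is planned for the retrospective NMCSD chart review: "A multivariate logistic regression model for predictors of MRSA will then be developed using a backward stepwise approach using Stata software".

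The end of Section VII sizes the objective: "For a power at 80%, alpha of 0.05, and examining 20 potential predictors with an R^2 of 0.10", which leads to 205 patients. It then adds: "As we examined more predictors, a larger sample size (500 to 550) is preferred".

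The documents do not state the p-value at which a term stays in the model, any adjustment for the number of candidates, any internal validation or shrinkage, or that the results are exploratory. The objective is labelled secondary.

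**The concern.** Backward elimination starts with every candidate and drops terms until all that remain pass a threshold. The p-values, odds ratios and intervals of the final model are then read as if that model had been chosen in advance. With many candidates and few events, some null candidates pass by chance, and those that pass do so because their estimates happen to be large.

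The stated aim is to determine the predictors, and the objective has its own sample size calculation, so the surviving terms are a planned result. Section IV reports the group's earlier multivariate model in that way, with the factors that remained described as significant predictors. A false term from this study would probably be presented in the same manner and with a sizeable odds ratio.

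**Working it through.** **Inputs.** From Section VII: 20 candidates, alpha 0.05, power 80%, R² 0.10, 550 enrolled, 500 followed, 10% colonized. That gives 0.10 × 500 = 50 to 0.10 × 550 = 55 colonized participants, or 50/20 = 2.5 to 55/20 = 2.75 events per candidate. Assumed: retention at p<0.05, since no level is stated.

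**1. The plan's own figure.** An overall F test of 20 predictors has f² = 0.10/0.90 = 0.1111. With noncentrality f² × N, the smallest N with power of at least 0.80 is 205 (power 0.8005). The plan's 205 is reproduced exactly. In that calculation, 0.05 is the level of one test of the whole set, not a rule for keeping a single predictor.

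**2. Simple bound.** For 20 independent null candidates, each kept at 0.05:
- P(at least one kept) = 1 − 0.95^20 = 0.64
- expected number kept = 20 × 0.05 = 1.0

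**3. Simulation of the stated method.** Backward elimination in logistic regression by Wald p-value, all candidates null, 2,000 runs per setting (Monte Carlo standard error about 0.01). Binary candidates have an assumed 30% prevalence.

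| Patients | Candidates | Event rate | Retention level | P(at least one kept) | Mean kept |
|---|---|---|---|---|---|
| 550 | 20 continuous | 10% | 0.05 | 0.64 | 1.02 |
| 550 | 20 binary | 10% | 0.05 | 0.62 | 0.98 |
| 550 | 20 binary, underlying correlation 0.5 | 10% | 0.05 | 0.64 | 1.15 |
| 500 | 20 binary | 10% | 0.05 | 0.61 | 0.96 |
| 550 | 20 binary | 15% | 0.05 | 0.64 | 1.02 |
| 550 | 20 binary | 5% | 0.05 | 0.56 | 0.83 |
| 550 | 30 binary | 10% | 0.05 | 0.76 | 1.52 |
| 550 | 20 binary | 10% | 0.01 | 0.14 | 0.16 |
| 550 | 20 binary | 10% | 0.10 | 0.88 | 2.00 |
| 550 | 20 binary | 10% | 0.20 | 0.98 | 4.07 |

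A separate run at 500 patients and 50 events gave 0.63 at the 0.05 level and 0.87 at 0.10.

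**4. Size of the false effects.** For one binary candidate at 30% prevalence with 50 events and 450 non-events, the variance of the log odds ratio is about 1/(50 × 0.3 × 0.7) + 1/(450 × 0.3 × 0.7) = 1/10.5 + 1/94.5 = 0.106, so the standard error is about 0.325. A harmful-looking null term is kept only if its odds ratio exceeds about exp(1.96 × 0.325) = 1.9. In simulation, retained null terms had a median odds ratio of about 2.2, counted in whichever direction they pointed. A true odds ratio of 1.5 was kept in 26% of runs, with a median estimate of 2.1.

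**5. Events for the infection outcome.** Section VII cites 13 per 1,000 person-years in one cohort and 40 per 1,000 at NMCSD in 2005. Over 500 × 2 = 1,000 person-years that is roughly 13 to 40 infections, fewer than the colonization events.

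**The case against.** The strongest reply is that the documents never say predictors are declared at an unadjusted 0.05. A reader might infer that rule from "alpha of 0.05, and examining 20 potential predictors", but step 1 shows that this alpha belongs to a test of the whole set. This stands: the 62 to 64% is conditional on an assumed level, and it should not be described as a multiple of a stated error rate. The missing level is itself a gap, because it could be settled after the data are seen.

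A reader might also infer one selection per outcome and combine two models into a higher rate, 1 − (1 − 0.62)² = 0.86. Section 3.2(b) names two outcomes, but Section VII speaks of a single model, and two models in the same patients would not be independent. The figure for one model is the one to use.

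Section IV says risk-factor data may help future preventive strategies. That sentence concerns the retrospective chart review, whose main results are to be descriptive. It is not evidence that a predictor from the prospective objective would be acted on.

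Pure noise is also not a realistic description of this setting, since Section IV reports earlier associations. That is fair, but it only lowers the count. If, for illustration, 5 of 20 candidates had real effects, the other 15 would still give 1 − 0.95^15 = 0.54 and 15 × 0.05 = 0.75 false terms on average.

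Finally, intervals for real effects are not badly affected: simulated coverage was 91% at a true odds ratio of 1.5 and 95% at 2.0. The harm lies in false and exaggerated predictors, not in intervals that are too narrow throughout.

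**Conclusion.** The concern holds in conditional form. The stated method is backward selection among 20 or more candidates with about 2.5 to 2.75 colonization events per candidate, and nothing in the plan guards against or labels chance findings. If 0.05 is the retention level, 20 null candidates give at least one predictor in about 62 to 64% of analyses, about one false term on average, with apparent odds ratios near 2. The rate falls to about 0.14 at p<0.01 and rises to about 0.87 at p<0.10. It also rises with more candidates (0.76 with 30).

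These figures rest on the assumed retention level, Wald-based elimination, a 10% event rate and, for the odds ratios, 30% prevalence of the candidate factor. The aim is secondary and observational. Nothing here bears on the randomized comparison, and the documents do not support reading it that way. The point merits a change to the plan because a better analysis of the same data is available.

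**What to change.** In Section VII, replace stepwise selection as the basis for naming predictors with a short list fixed in advance from the associations reported in Section IV, entered together without selection:

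- **Colonization:** low CD4 count, TMP/SMX use, recent antibiotic use, hospitalization. Four terms on 50 to 55 events is about 12.5 to 13.75 events per term.
- **Infection:** CD4 count, HIV viral load, TMP/SMX use, MSM or injection drug use, history of syphilis, and beta-lactam exposure. The last two must be included because they were the factors left in the NMCSD multivariate model. Six terms on 13 to 40 infections is about 2.2 to 6.7 events per term. The plan should therefore say how the list will be shortened in proportion to the infections observed, and use a penalized fit such as Firth if they are few.

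Report all other candidates, and the retrospective stepwise model, as exploratory, with bootstrap selection frequencies and no claim of significance. State the retention level of any stepwise model that is kept.

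Holm across each short list is optional. Without it, the chance of at least one false positive is about 1 − 0.95^4 = 0.19 for four independent null terms and 1 − 0.95^6 = 0.26 for six. A forced-entry model with Holm gave about 0.04 in simulation.

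The cost is a revised paragraph, slightly more analysis, and fewer factors called significant predictors. No new patients or data are needed: Section 6.3 already collects medications, hospitalizations, sexually transmitted diseases, sexual activity, drug use and HIV markers.

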Patients will be asked to report to their enrolling HIV clinic for any soft tissue infections or any infection thought to be secondary to MRSA; if able, cultures of the wound site will be obtained. Blood cultures will be obtained at the primary provider's discretion depending on the presence of fevers, toxemia, and the extent of soft tissue involvement. Patients will also have repeated screening for colonization including nares, throat, groin, axilla, and perirectal swabs (5 total swabs) at this time. CD4 counts and an HIV viral load will be obtained at the time of the soft tissue infection or with any MRSA infection for patients presenting to the enrolling site. Patients with positive wound culture and/or blood cultures for MRSA will be classified as a "MRSA infection." Those with a soft tissue infection without positive cultures from these sites will be classified as a "Soft Tissue Infection NOS." The patient will be treated with intravenous or oral antibiotics and/or surgical procedures at the discretion of the medical provider that the patient presents to for evaluation. Patients who have an infection while located remotely from the HIV clinic will be given a contact information card and will be asked to call the site PI or study coordinator at their enrolling site to notify them of the infection. The site PI or study coordinator will try to arrange for the aforementioned tests to be performed at the local medical clinic; CD4 counts and HIV viral loads will not be performed for patients presenting remotely to the enrolling site. In addition, coordinators will gather information on the tests and treatments performed. Patient questionnaires will be completed for patients experiencing a soft tissue infection or MRSA infection (refer to case report forms).

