The sample size calculation for this study is based on the primary objective of the study which is to evaluate the effectiveness of decolonization procedures with application of nasal mupirocin (Bactroban®) and hexachlorophene (pHisoHex®) soaps compared to placebos with no antibacterial activity among patients found to be colonized with MRSA in the prevention of future colonization with MRSA. We will also examine the number of infections with MRSA and soft tissue infections as secondary measures of the primary objective.

The rate of MRSA colonization of the nares was 1% in a recent study involving the general US population [41]. Among HIV-infected patients this rate is higher, with one study showing a carriage rate of 27.6% [11]. However, other studies had rates of 3-9% among their HIV-infected patients [26, 27, 42]. The MRSA infection rate among HIV-infected persons is approximately 13 cases/1000 person-years in one study that examined 3,455 patients over three years with 94 MRSA infections [7]; our rate at NMCSD appears higher with 40 cases/1000 persons in the year 2005 [12].

In a study examining both MSSA and MRSA colonization rates, after treatment with mupirocin (Bactroban®), colonization was eradicated in 93%, whereas 85% who received placebo remained colonized ($P < .001$). At day 90 after study entry, 61% of the residents in the mupirocin group remained decolonized [36]. In a study by Ellis et al involving 812 soldiers over a 8-10 week period of training, of those with MRSA colonization without treatment for decolonization, 38% developed a soft tissue infection [43].

Using these data, assuming 10% of the HIV patients would be colonized, that half would be randomized to each treatment group, and that 85% in the non-treatment arm would remain colonized versus 7-39% (mean 23%) of the treated would remain colonized, we calculated the following sample sizes:

Colonization rate of the	Power	Alpha level	Sample size per group	Total sample size
--------------------------	-------	-------------	-----------------------	-------------------

Treated Group				
0.07	.80	.05	80	160
0.23	.80	.05	120	240
0.39	.80	.05	210	420

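### Section VII gives a 1-way ANOVA with no patient term for same-patient CD4 and viral-load values, and its incidence formula counts infections where secondary objective (a) asks for colonisation

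*Combined protocol and SAP*

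**What the plan says.** **Objective (c).** Section 3.2 states the aim: "To evaluate the change in CD4 counts and HIV viral loads during the time of a MRSA or soft tissue infection". Section VII gives the analysis: "change in the CD4 count and/or viral load pre- versus during a MRSA infection we will utilize a 1-way ANOVA". It then adds two further comparisons, before infection with after resolution and during infection with after resolution, and names no method for either. Nothing in the document mentions a paired test, a patient effect or a repeated-measures model for these data.

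**Objective (a).** Section 3.2 states the aim: "To determine the prevalence and incidence of MRSA colonization of the nares, throat, perirectal, axilla, and groin areas among HIV infected patients". Section VII defines prevalence by counting colonised patients, but in the same sentence defines "the incidence as the number of new infections per calendar time divided by the total population studied". Section 6.3 makes infection a separate event, established by culture of a wound or of blood and not by a surveillance swab: "Patients with positive wound culture and/or blood cultures for MRSA will be classified as a" case of MRSA infection. Question (1) of Section VII also analyses colonisation and infection separately.

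The nearest thing to an acquisition analysis is question (4): "A Kaplan-Meier long-rank test will be conducted on three groups: initially negative", followed by the two randomised groups. It belongs to the primary objective and is not assigned to objective (a).

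**The concern.** A change from before to during to after an infection is a within-patient quantity. An ordinary 1-way ANOVA treats the periods as independent groups, so the stable differences between patients go into the error term. A real fall in CD4 or rise in viral load could then be missed, in a data set that will probably be small. Section VII also mentions only MRSA infection, while Section 6.3 collects CD4 and viral load at soft tissue infection visits as well. Those data serve a stated objective but have no stated analysis.

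For objective (a), an analyst who follows the formula literally reports an infection rate and no colonisation incidence.

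**Working it through.** The plan states no sample size, power or alpha for objectives (a) or (c), so there is no figure of its own to reproduce.

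**Objective (c): expected number of events.** Section VII cites one rate in these terms: "The MRSA infection rate among HIV-infected persons is approximately 13 cases/1000 person-years in one study". It also cites 40 per 1000 at one site in 2005, and it expects 500 participants to be followed for two years.

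- 500 × 2 × 0.013 = 13 MRSA infections
- 500 × 2 × 0.040 = 40 MRSA infections

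Soft tissue infections would add to this. Thirty pairs lies within the 13 to 40 range.

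**Objective (c): cost of ignoring the pairing.** Let n patients each give one value before and one during infection, with equal SD and correlation ρ. The unpaired test uses variance 2·SD²/n for the mean difference. The true variance is 2·SD²·(1 − ρ)/n. For large samples:

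- True type I error = 2·[1 − Φ(1.96/√(1 − ρ))], which is 1.9%, 0.56% and 0.035% at ρ = 0.3, 0.5 and 0.7.
- Where a paired test has 80% power, unpaired power ≈ Φ(2.80 − 1.96/√(1 − ρ)), which is 68%, 51% and 22%.

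Simulation with 30 complete pairs (normal data, two-sided 5%, 40,000 runs; ρ and effect size are assumed, since the documents give neither):

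| ρ | Type I error, unpaired | Power at 0.3 SD, unpaired v paired | Power at 0.6 SD, unpaired v paired |
|---|---|---|---|
| 0.05 | 4.3% | 20 v 21% | 63 v 63% |
| 0.3 | 2.1% | 16 v 27% | 66 v 77% |
| 0.5 | 0.7% | 13 v 36% | 68 v 89% |
| 0.7 | 0.1% | 8 v 54% | 71 v 98% |

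With 13 pairs and 0.3 SD, power at ρ = 0.3, 0.5 and 0.7 is 8 v 14%, 5 v 17% and 3 v 25%.

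**Objective (c): values below the assay limit.** The table assumes uncensored normal data. With 30 pairs, 0.3 SD and ρ = 0.5, power falls from 13 v 36% to about 11 v 26% when half of the pre-infection values are below the limit. At 80% below the limit it is 7 to 8% v 14%. The censored shares are assumptions.

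**Objective (c): incomplete sets.** With 30 pre-infection values, 20 during-infection values and missingness at random, power at 0.3 SD for the unpaired test, the strict paired test and a random-intercept model is 13/18/20%, 12/24/27% and 9/38/40% at ρ = 0.3, 0.5 and 0.7.

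**Objective (a), read literally.** The numerator is a different event from the one in the objective, so no correction ratio applies. The quantity is simply not defined.

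**Objective (a), if infections was meant to read colonisations.** Let p be the share colonised at baseline and D the number of first acquisitions, all of which arise among the N(1 − p) baseline-negative participants. Dividing D by N where N(1 − p) is needed gives a ratio of 1 − p, counting baseline carriers alone.

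| Source of p | p | Ratio |
|---|---|---|
| Section VII, 10% over the study period | 10% | 0.90 |
| Section 5.2, approximately 10-15% carrying MRSA | 10-15% | 0.90-0.85 |
| Section 5.2, 38 + 38 treated of 550 (76/550) | 13.8% | 0.86 |
| Section VII, several other HIV cohorts | 3-9% | 0.97-0.91 |
| Section VII, one other HIV cohort | 27.6% | 0.72 |

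The fourth row rests on this text: "other studies had rates of 3-9% among their HIV-infected patients". The first three rows are the plan's own assumptions. None is clearly a baseline figure. Where part of the carriage is acquired later, the ratio is nearer 1.

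**The case against.** For (c), the best defence is incomplete wording. A significant change over pre, during and after can only be within-patient, and a one-way repeated-measures ANOVA fits three periods. That is plausible, and if it was meant the sponsor need only say so. The text as it stands does not say it.

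For (a), the Precis and Section IV make the incidence of both colonisation and infection a study aim, so an infection formula serves a stated purpose. This stands: the formula is not misplaced in the study, and the gap is the missing colonisation definition. Question (4) can also give cumulative acquisition in the initially negative group, but that is not a rate.

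Four stronger readings are tempting, and the documents do not support them:

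- *The ANOVA produces false positives.* With one episode per patient the error runs the other way. Repeat infections in one patient would be a further, unmodelled dependence.
- *The two incidence faults add.* They are alternatives: either the wrong event is counted, or the right event has too wide a denominator. The understatement applies only to first acquisition, since cleared carriers can acquire MRSA again and belong in the denominator of an all-acquisition rate.
- *The power figures carry over to any viral-load analysis.* They hold for CD4 or mostly detectable log10 viral load, and the gain shrinks with censoring.
- *A mixed model is required.* Nearly all the gain comes from pairing. In the incomplete-data runs above, the mixed model adds about 2 points over a strict paired test.

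**Conclusion.** Both points hold as written, for secondary objectives only. For (c), the stated test is conservative. At moderate correlation it loses from about ten percentage points of power (ρ = 0.3) to several tens (ρ = 0.7), and at correlations near zero almost nothing. These sizes rest on an assumed correlation, effect size and number of pairs. At the low end of expected events even the correct test is weak, so the change makes better use of sparse data and does not rescue an underpowered objective. That two comparisons have no stated method and that soft tissue infections are left out needs no assumption.

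For (a), no colonisation incidence follows from the formula. On the alternative reading, a first-acquisition rate would be 10 to 15% too low if all the carriage that the plan assumes is present at baseline, and less if not. The documents do not settle which. The change should be made before analysis.

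**What to change.** **Objective (c).** State a within-patient analysis for all three comparisons: a paired test or a repeated-measures ANOVA. If the latter was intended, say so. A linear mixed model with a patient random effect and period as fixed effect is an option that keeps patients with incomplete sets. Analyse viral load on the log10 scale with a stated rule for values below the assay limit. Cover MRSA and soft tissue infections. State the time windows for the pre and after values and how repeat infections in one patient are handled.

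**Objective (a).** Define colonisation incidence as first MRSA-positive surveillance swabs per person-year at risk among baseline-negative participants, with exact Poisson limits. If re-acquisition after clearance is wanted, report it as a separate rate whose denominator includes cleared carriers. Report infection incidence separately, per person-year of follow-up.

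**Cost.** A few sentences in Section VII and no new data collection, since the six-monthly five-site swabs already supply the colonisation data. One limit remains for (c). Under Section 6.3, CD4 and viral load are drawn only at infection visits and not for patients who present remotely, and other values come from record review. Some sets will therefore be incomplete.
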